11.4.2 Analyses of efficacy endpoints

11.4.2.1 Analysis of primary efficacy endpoint(s)

Five common skeletal manifestations of Gaucher disease will be summarized separately. A single composite endpoint will not be constructed.

1. Mobility, bone crisis and pain: Category of mobility status and bone pain, as well as number of new bone crises, will be summarized. Additionally shifts in category of mobility and pain from study and eliglustat baseline will be presented.
2. Bone marrow infiltration: Bone marrow infiltration score will be summarized both continuously and categorically. Reported values and changes from study and eliglustat baseline will be summarized as data is available.

Category of infiltration score will be constructed and summarized:

Mild: 0 to 4

Moderate: 5 to 8

Severe: 9-16

Shifts in category from study and eliglustat baseline will be summarized.

1. BMD: Bone mineral density in (g/cm²), as well as T and Z scores, will be summarized by time point as well as absolute and percent changes from study and eliglustat baseline.
2. Lytic lesions, fractures, infarctions and osteonecrosis. Incidence of new or worsening lytic lesions, new or worsening AVN, new or worsening infarctions and new fractures will be summarized at the 2 year and end of study time points. Annual incidence rates may also be calculated and summarized.
3. Bone biomarkers: Levels of P1NP, CTx and MIP 1 β , as well as absolute and percent changes from study or eliglustat baseline will be summarized.

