9.5 APPROPRIATENESS OF MEASUREMENTS

9.5.1 Primary endpoint

The primary endpoint, bone disease, will be assessed using measurements that have been validated for Gaucher disease or for other more common bone conditions.

Gaucher disease clinical assessments (mobility, bone pain and bone crisis) are established clinical parameters of bone lesions in Gaucher disease ([8](#)).

Magnetic Resonance Imaging is an established procedure to evaluate bone marrow not only for Gaucher disease, but also in oncology ([20](#)). It avoids the exposure to ionizing radiations observed with computerized tomography. A semi-quantitative method of measuring bone marrow infiltration by MRI has been developed and validated ([18](#)). It requires only standard equipment. Therefore, it can be implemented in study sites worldwide. Central reading of the images by trained readers will increase the quality and decrease the variability of the results.

Bone MRI also allows detecting lytic lesions, osteonecrosis, infarction and fractures.

Bone MRI will be performed yearly, a standard frequency in patients who are expected to be stable after multiple years of eliglustat treatment.

Dual-energy X-ray absorptiometry is the gold standard to measure BMD. A yearly frequency has been established as the time necessary to see significant changes in BMD.

Femur and spine X-Ray will serve mainly as references for additional follow up of the patients once they have left the study, when MRI may not be widely available or traditionally used to follow patients.

Bone biomarkers

Total procollagen type 1 N-terminal propeptide (P1NP), a marker of bone formation, and C-terminal telopeptide of type 1 collagen (CTX), a marker of bone resorption, have been recommended as reference markers of fracture risk assessment in age related osteoporosis by a working group of the International Osteoporosis Foundation and the International Federation of Clinical Chemistry and Laboratory Medicine (21).

MIP1 β has been shown to display moderate sensitivity and specificity to detect osteonecrosis in Gaucher disease (22).

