11.4 STATISTICAL METHODS

All endpoints will be summarized descriptively; no hypothesis testing will be performed. Descriptive statistics include those for continuous (n, mean, median, minimum, maximum), categorical (n, percent), cumulative incidence (n, percent) or incidence rate (n/year) outcomes, as appropriate. Calculations and summaries will include all non-missing data at a given time point, imputation will not be performed.

Analysis will be performed on safety and efficacy endpoints at 2 points in this study:

- After the last patient enrolled has completed 2 years of treatment (two-year analysis period)
- When the study is complete

For the PAP, response will be calculated both in reference to study entry (study period) and to first eliglustat treatment (eliglustat treatment period). Because patients will enter this study having been treated with eliglustat for various durations, two baselines will be used:

- Study baseline, defined as status at study entry; and
- Eliglustat baseline, defined as status at first dose of eliglustat in the previous Phase 2 or Phase 3 study.

In reference to the study period, skeletal response will be evaluated for all patients at the 2 year point by measured values (eg, category of bone pain, or bone density value in g/cm²) and changes from baseline (eg, shift in category of bone pain or absolute and percent change from baseline in BMD g/cm² or incidence over 2 years, as appropriate).

In reference to the period of eliglustat treatment, skeletal response will be evaluated 2 years after study entry, but results will be grouped by duration of eliglustat treatment at the time of analysis. The actual groupings will depend on the distribution of treatment duration at the time of analysis, eg, 6 yr., 7 yr., 8 yr. or 6-8 yr., 8-10 yr.

When the study has completed, summaries will be performed for both the total on-study period, and the eliglustat treatment period, as described above.

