11.4.2.2 Analyses of secondary efficacy endpoints

Biomarker: Biomarkers will be summarized as measured values, absolute and percent change from eliglustat and study baseline.

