#### **2.4.4 Analyses of efficacy endpoints**

In reference to the study period, efficacy result will be evaluated for all patients at the 2 year point by measured values (eg, category of bone pain, or bone density value in g/cm^2) and changes from baseline (eg, shift in category of bone pain or absolute and percent change from baseline in BMD g/cm^2 or incidence over 2 years, as appropriate).

In reference to the period of eliglustat treatment, efficacy result will be evaluated 2 years after study entry, but results will be grouped by duration of eliglustat treatment at the time of analysis. The actual groupings will depend on the distribution of treatment duration at the time of analysis (eg,  $\leq 5$  years versus  $>5$  years).

When the study has completed, summaries will be performed comparing to the 2 baselines as described above if applicable.

All efficacy endpoints will be summarized descriptively; no hypothesis testing will be performed. In general, descriptive statistics (number, mean, standard deviation, minimum and maximum) of the absolute value, change from baseline and/or percentage change from baseline for continuous endpoints will be analyzed. Summary statistics (count, percentage) will be summarized for the categorical endpoints. Cumulative incidence (n, percentage), incidence rate (n/year), or other descriptive statistics will also be displayed as appropriate. Calculations and summaries will include all non-missing data at a given time point, imputation will not be performed.

By-patient data listings containing efficacy endpoints will be produced if necessary.

All the below mentioned other efficacy endpoint analyses will be produced for the full analysis population. Refer to [Section 2.5.3](#) for details on handling dropouts, missing data, and patients who have more than one value assessed within the same time frame.

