#### **2.4.4.1.5 Bone biomarkers**

Absolute values, change and percent change from baseline (study baseline and eliglustat baseline) for levels of P1NP, CTx and MIP 1  $\beta$  will be summarized by visit.

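### For the six biomarkers, SAP 2.4.4 summarises percent change by an arithmetic mean without the median that Protocol 11.4 lists; if within-patient variability is about 30% or more, this mean materially overstates rises and understates falls

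*Protocol*

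**What the plan says.** Three layers of text govern how change in the markers is reported.

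- **What is summarised (protocol).** Protocol 11.4.2.1 asks for levels of P1NP, CTX and MIP-1β, "as well as absolute and percent changes from study or eliglustat baseline will be summarized". These markers form one of the five primary skeletal domains. For the GD1 markers, Protocol 11.4.2.2 says: "Biomarkers will be summarized as measured values, absolute and percent change from eliglustat and study baseline".
- **Which statistics (protocol).** Protocol 11.4 sets the general list: "Descriptive statistics include those for continuous (n, mean, median, minimum, maximum". The median is on it.
- **Which statistics (SAP).** SAP 2.4.4 gives, for continuous efficacy endpoints in general, "descriptive statistics (number, mean, standard deviation, minimum and maximum) of the absolute value, change from baseline and/or percentage change from baseline". The SD has been added and the median is gone. SAP 2.4.4.1.5 then plans, by visit, "Absolute values, change and percent change from baseline (study baseline and eliglustat baseline) for levels of P1NP, CTx" and MIP-1β. SAP 2.4.4.2 does the same for the GD1 markers and also shows them separately for CYP2D6 ultra-rapid metabolisers.

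SAP 1.5 reports no modification to the protocol's statistical section, and SAP 1.6 lists only the treatment-emergent period. Elsewhere the SAP does name the median: in 2.4.4.1.4 (bone lesions), 2.4.4.4 (organ volumes, hemoglobin, platelets) and 2.4.5.3 (laboratory variables). Neither document plans a log transformation, a geometric mean or a ratio to baseline for any of the six markers.

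**The concern.** A percent change in a positive marker cannot fall below -100% but has no upper limit. Averaging such values arithmetically gives rises more weight than falls of the same relative size. Noise in the denominator adds to this: for these markers each baseline is a single last value before dosing (SAP 2.4), whereas SAP 2.5.2 averages two values for hemoglobin and platelets in patients from the Phase 2 and ENCORE studies.

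The study has no control arm in which the asymmetry could cancel, and it does no testing, so the descriptive statistic is the result the reader takes away. Patients enter after roughly 4 to 8 years on eliglustat (Protocol 11.1). If the typical change from study baseline is small, a shift of a few points can determine its apparent direction. Against eliglustat baseline, where falls would be looked for in MIP-1β and the GD1 markers, the same shift makes the typical relative fall look smaller. The median would largely avoid this, and it is the statistic missing from the SAP's list.

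**Working it through.** **No plan figure to reproduce.** The documents state no biomarker CV or SD, no sample size calculation and no power. What can be computed is the gap between the arithmetic mean percent change and the typical (geometric or median) change.

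**Inputs**
- n = 32: approximate enrolment, Protocol 11.1.
- Within-patient CV per measurement, c: *assumed*, 10% to 50%.
- Markers log-normal, with equal independent error at baseline and follow-up: *assumed*.
- Illustrative falls f: 43.5% and 80%. The 43.5% is borrowed from the MIP-1β result in Protocol section 4. That figure is an LS mean treatment difference against placebo, not a within-patient change, so it only sets a plausible scale. The 80% is arbitrary.

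**Simple check.** One patient doubles (+100%) and one halves (-50%). The mean is (100 - 50)/2 = +25%. The geometric mean ratio is √(2 × 0.5) = 1, which is no change.

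**General formula.** Let R = follow-up/baseline, with median 1 - f and SD(ln R) = s. Then

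E[mean percent change] = (1 - f) × exp(s²/2) - 1.

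With CV c at each of two measurements, s² = 2 ln(1 + c²), so exp(s²/2) = 1 + c². Hence:

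- stable cohort (f = 0): expected mean percent change = c²;
- true fall f: expected mean percent change = (1 - f)(1 + c²) - 1.

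Example at c = 0.30: stable, 0.30² = +9.0%; 43.5% fall, 0.565 × 1.09 - 1 = -38.4%.

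The two right-hand columns below come from 20,000 simulated stable cohorts of 32.

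| Assumed CV | Stable cohort, expected mean % change | 43.5% fall shows as | 80% fall shows as | Sampling SD of the mean (points) | Stable cohorts with mean above 0 |
|---|---|---|---|---|---|
| 10% | +1.0% | -42.9% | -79.8% | 2.5 | 64% |
| 20% | +4.0% | -41.2% | -79.2% | 5.2 | 77% |
| 30% | +9.0% | -38.4% | -78.2% | 8.3 | 86% |
| 40% | +16.0% | -34.5% | -76.8% | 12.0 | 92% |
| 50% | +25.0% | -29.4% | -75.0% | 16.5 | 95% |

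An unbiased summary would be above zero in about 50% of stable cohorts.

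**Reading the table**
- At CV 10% to 20% the shift is 1 to 4 points, less than the sampling SD of 2.5 to 5.2. At CV 30% it is 9.0 against 8.3, so it is no longer lost in sampling error.
- The shift does not depend on n. It is the same in the treatment-duration groups and the ultra-rapid metaboliser subset, only with more sampling error around it.
- Real differences between patients in their change also add to s. For example, s = 0.5 gives exp(0.125) - 1 = +13.3% with no typical change.
- For large falls the distortion is small in points: at most 5 for an 80% fall at CV 50%.

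**Alternatives under the same model.** In stable cohorts the geometric mean change and the median percent change both averaged between 0.0% and +0.9% for CVs of 10% to 50%. Mean absolute change stayed within 0.3% of the baseline mean (assuming a between-patient SD of 0.8 on the log scale).

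**The case against.** The case against is substantial, and most of it stands.

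- **The percentage is not the only summary.** A reader might infer that the plan rests on the mean percent change. It does not: measured values and absolute changes are planned at every visit for both baselines, and they do not carry this bias. They would appear beside any inflated percentage. They do not fully replace a sound relative summary, because a mean absolute change is dominated by patients with high levels when levels differ widely.
- **The protocol has the median.** A reader might infer that the whole plan overlooked the problem. Protocol 11.4 lists the median and the SAP declares no departure, so the SAP's list may be a slip. SAP 2.4.4 also says *in general* and allows other descriptive statistics. SAP 2.4.5.3 plans medians for central and local laboratory values, and biomarkers are the centrally run laboratory tests. However, SAP 2.1.4.3 does not include biomarkers among the laboratory safety variables, so that route is uncertain.
- **The size is assumed.** It is tempting to say that P1NP and CTX would both appear to rise. The documents do not support this: they give no CV, and at CV 10% about 36% of stable cohorts (100% - 64%) would still show a mean at or below zero.
- **Stability of the biomarkers is not asserted.** Protocol 9.5.1 speaks of "a standard frequency in patients who are expected to be stable after multiple years of eliglustat treatment", but that justifies yearly bone MRI and says nothing on biomarker change. A stable cohort is a scenario here, not a documented expectation for these markers.
- **No decision hangs on it.** There is no test, threshold, responder rule or composite. The arithmetic mean percent change is also a valid description of itself; it is biased only as a description of the typical relative change.

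What survives is that the SAP's list for these endpoints omits, undeclared, the one protocol statistic that describes typical relative change with little distortion, and offers no log-scale alternative.

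**Conclusion.** The point holds as an asymmetry in one of several planned summaries, together with an undeclared difference between the SAP and the protocol. Under log-normal markers with equal independent error at both time points, the mean percent change in a cohort with no typical change is expected at +1% to +4% for CVs of 10% to 20%, which is minor. It is +9% at 30% and +16% at 40%, which is material for a cohort of about 32. A typical fall of 43.5% would show as 41.2%, 38.4% or 34.5% at CV 20%, 30% or 40%. The direction follows from the arithmetic; the size rests on a CV the documents do not give.

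The documents do not support the stronger conclusion that the biomarker result as a whole would be an artefact, or that the arithmetic percent change must be removed. The consequence is one of interpretation. In a single-arm, descriptive study that is enough to justify a change this cheap.

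**What to change.** 1. **SAP 2.4.4:** add the median, with quartiles, to the statistics for continuous efficacy endpoints, so that the list agrees with Protocol 11.4.
2. **SAP 2.4.4.1.5 and 2.4.4.2:** for the six markers, add the geometric mean ratio to study baseline and to eliglustat baseline as the main relative summary. Compute it as exp(mean of ln(value/baseline)) - 1, shown as a percent with a 95% CI. The interval describes precision only; it implies no test and does not itself address the asymmetry.
3. **Keep** the measured values, absolute changes and arithmetic percent changes alongside, for continuity with the feeder studies.
4. **SAP 1.6:** record the geometric mean ratio as an addition.

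Existing data rules already suit the log ratio. SAP 2.5.1 sets values below quantification to the limit, so logarithms exist. The doubling of chitotriosidase for heterozygous patients (SAP 2.1.3.2.1) cancels when it is applied at both time points.

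The cost is a few lines of SAP text and one extra set of table rows. No new data are needed. The geometric figures will differ in form from any arithmetic percent changes in the feeder-study reports, which is why both should be shown.

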11.4.2.2 Analyses of secondary efficacy endpoints

Biomarker: Biomarkers will be summarized as measured values, absolute and percent change from eliglustat and study baseline.

11.4.3 Analyses of safety data

Adverse experience will be coded using the Medical Dictionary for Regulatory Activities (MedDRA) Version 18.0 or higher; all adverse experiences will be summarized by body system and MedDRA preferred term overall, by relationship and severity and seriousness. All deaths will be summarized.

Physical examinations, routine laboratory assessments (chemistry and hematology), biomarkers and pregnancy testing for female patients of childbearing potential will be summarized at each

time point. Additionally, the change from study baseline and/or eliglustat baseline, as appropriate, may be summarized. Concomitant medications will be reported.

Observation period

The observation of safety data will be as follows:

- Screening is from signed informed consent to the day before the 1st dose of IMP is administered.
- TEAE observation period is from first to last dose of IMP in this study. Patients with an SAE or AESI should be followed until resolution or when follow-up is no longer considered medically necessary, or the patient is lost to follow-up.

All safety analyses will be performed on the Safety population using the following common rules:

The baseline value is defined generally as the last available value before first dose of IMP in this study.

Adverse event incidence tables will present by system organ class (SOC) (sorted by internationally agreed order), preferred term (PT) sorted by decreasing frequency for each treatment group, the number (n) and percentage (%) of patients experiencing an AE. Multiple occurrences of the same event in the same patient will be counted only once in the tables within a treatment Phase. The denominator for computation of percentages is the safety population within each treatment group.

AE incidence tables for the AESIs below will be generated.

- Clinically significant cardiac arrhythmias detected by ECG or Holter monitoring that do not meet criteria for an SAE.
- Syncope from any cause.

Death: The following deaths summaries will be generated:

- Number (%) of patients who died and reasons for death if collected in death report form summarized on the safety population
- All AEs leading to death (death as an outcome on the AE CRF page as reported by the Investigator), by primary SOC and PT, showing number (%) of patients sorted by internationally agreed order of SOC and alphabetic order of PT
- TEAE leading to death (death as an outcome on the AE CRF page as reported by the Investigator) by primary SOC and PT showing number (%) of patients sorted by internationally agreed order of SOC and alphabetic order of PT.

11.4.4 Analyses of pharmacokinetic and pharmacodynamic variables

A listing of Genz-99067 plasma concentrations will be provided.

11.4.5 Analyses of Patient Reported Outcomes (Health-related Quality of Life/health economics variables)

The SF-36 Health Status Survey Version 2 is made up of 36 questions, each of which has a weighted response associated with it. The 36 questions are combined into various groupings to form eight scales, which are then further combined to form two overall summary measures, the Physical Component Summary (PCS) and Mental Component Summary (MCS). These will be generated and summarized at each visit, as well as changes from eliglustat and study baseline, as described in the statistical analysis plan.

12 ETHICAL AND REGULATORY CONSIDERATIONS

12.1 ETHICAL AND REGULATORY STANDARDS

This clinical trial will be conducted by Genzyme, the Investigator, delegated Investigator staff and Sub investigator, in accordance with the principles laid down by the 18th World Medical Assembly (Helsinki, 1964) and all applicable amendments laid down by the World Medical Assemblies, and the ICH guidelines for good clinical practice (GCP), all applicable laws, rules and regulations.

This clinical trial will be recorded in a free, publicly accessible, internet-based registry, no later than 21 days after the first patient enrollment, in compliance with applicable regulatory requirements and with Sponsor public disclosure commitments.

12.2 INFORMED CONSENT

The Investigator (according to applicable regulatory requirements), or a person designated by the Investigator, and under the Investigator's responsibility, should fully inform the patient of all pertinent aspects of the clinical trial including the written information giving approval/favorable opinion by the Ethics Committee (Institutional Review Board/Independent Ethics Committee (IRB/IEC)). All participants should be informed to the fullest extent possible about the study, in language and terms they are able to understand.

Prior to a patient's participation in the clinical trial, the written informed consent form should be signed, name filled in and personally dated by the patient or by the patient's legally acceptable representative, and by the person who conducted the informed consent discussion. A copy of the signed and dated written informed consent form will be provided to the patient.

The informed consent form used by the Investigator for obtaining the patient's informed consent must be reviewed and approved by Genzyme prior to submission to the appropriate Ethics Committee (IRB/IEC) for approval/favorable opinion.

The Investigator (according to applicable regulatory requirements), or a person designated by the Investigator, should fully inform the patient (and the parent[s] or guardian[s]) of all pertinent aspects of the clinical trial including the written information given approval/favorable opinion by the ethics committee (IRB/IEC). All participants should be informed to the fullest extent possible about the study in language and terms they are able to understand.

Prior to a patient's participation in the clinical trial, the informed consent form should be signed, name filled in and personally dated by the patient, and by the person who conducted the informed consent discussion.

The informed consent form and the assent form used by the Investigator for obtaining the Patient's Informed Consent must be reviewed and approved by the Sponsor prior to submission to the appropriate Ethics Committee (IRB/IEC) for approval/favorable opinion.

